2.3 Clinical Rationale

VOLUMA XC was designed specifically for volumizing and has demonstrated effectiveness in restoring age-related mid-face volume deficit (Jones 2013). The protocol is designed to collect safety and effectiveness data of VOLUMA XC injectable gel using cannula in subjects seeking correction of age-related volume deficit in the mid-face.

3. Study Objectives and Clinical Hypotheses

3.1 Study Objectives

The objective of this study is to evaluate the safety and effectiveness of VOLUMA XC injectable gel using cannula in subjects seeking correction of age-related volume deficit in the mid-face.

Approval Date: 19-Oct-2017

3.2 Clinical Hypotheses

The response to treatment in terms of the Mid-Face Volume Deficit Scale (MFVDS) change from baseline (screening) to Month 1 with cannula will be non-inferior to response to treatment with needle.

4. Study Design

4.1 Structure

This is a multicenter, evaluator-blind, randomized, within-subject controlled, paired-comparison study. Up to 7 investigational sites in the United States will enroll and follow subjects who meet the study criteria.

4.2 Duration

Each subject's participation will encompass 1 day of treatment and 3 months of follow-up.

4.3 Treatment Groups and Treatment Regimen

4.3.1 Study Treatment

VOLUMA XC injectable gel injected with a [REDACTED] cannula and an optional [REDACTED]

4.3.2 Control Treatment

VOLUMA XC injectable gel injected with a [REDACTED] needle

4.3.3 Methods for Blinding

The Evaluating Investigator (EI) will be blinded to treatment. The EI will not be present during the injection procedures. The Treating Investigator (TI), study coordinator, and subject will not be blinded to treatment, but they will secure the randomization and other records (eg, records of study treatments and prior study assessments) from potential discovery by the blinded EI. The TI will not discuss the randomized treatment assignments with or in the presence of the EI.

4.4 Permissible and Prohibited Medications/Treatments

4.4.1 Permissible Medications/Treatments

For the cheek treated with cannula, an anesthetic agent must be used on the treatment area prior to making the entry point with the introductory needle. For the cheek treated with needle, use of anesthesia is optional, according to routine practice, but it must be limited to the treatment area only. Acceptable topical and injectable anesthetic agents are listed in the investigational directions for use (IDFU).

[REDACTED]

The use of any concomitant medication, prescription or over-the-counter, is to be recorded on the subject's electronic case report form (eCRF) at each visit along with the reason the medication is taken.

Therapy considered necessary for the subject's welfare may be given at the discretion of the TI. If the permissibility of a specific medication/treatment is in question, please contact Allergan.

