7.4 Treatment Characteristics

Treatment characteristics will be evaluated by collecting information on anesthesia usage injection volume, and injection ease [REDACTED]

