12.4 Documentation

12.4.1 Source Documents

Source documents may include a subject's medical records, hospital charts, laboratory notes, device accountability records, investigator MFVDS assessments, subject questionnaires and diaries, clinic charts, the TI's subject study files, results of pregnancy tests, and results of any other diagnostic tests such as X-rays, laboratory tests, and magnetic resonance imaging. The SAE Form and Pregnancy Surveillance Form are also considered source documents. The TI's copies of the eCRFs serve as part of the TI's record of a subject's study-related data.

The following information is to be entered into the subject's medical record:

- Subject's name

- Subject's contact information
- Date that the subject entered the study and subject number assigned from IWRS
- Study title and/or the protocol number and study sponsor
- A statement that informed consent was obtained, including the date and a statement that HIPAA Authorization or other country and local subject privacy required documentation for this study has been obtained, including the date
- Details of the injection procedure including anesthetic used, volume injected, ease of injection, details regarding molding and massage, kit numbers of study device injected, subject's assessment of procedural pain
- Dates of all subject visits
- All concurrent medications (List all prescription and non-prescription medications being taken at the time of enrollment. At each subsequent visit, changes to the list of medications are to be recorded.)
- Occurrence and status of any AEs
- Date the subject exited the study, and a notation as to whether the subject completed the study or reason for discontinuation
- Results of laboratory tests performed by the site (eg, urine pregnancy tests)

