4.2 Study Objectives and Endpoints

The objective of this study is to evaluate the safety and effectiveness of VOLUMA XC injectable gel using cannula in subjects seeking correction of age-related volume deficit in the mid-face.

The study primary objective, secondary objective, and other objectives are presented with corresponding endpoint(s) below:

Table 4-1 Study Objectives and Corresponding Endpoints

Objectives	Endpoints	
To evaluate the safety and effectiveness of cannula versus needle for the correction of age-related volume deficit in the mid-face.	Primary Endpoint: • MFVDS response distribution by treatment, based on EI assessment on a 6-point scale of ordinal categories, from 0 to 5 (none, minimal, mild, moderate, significant, severe), for baseline and change from baseline to month 1 (primary endpoint)	
	 MFVDS responder rates by treatment, based on EI assessments on a 6-point scale of ordinal categories, from 0-5 (none, minimal, mild, moderate, significant, severe), with responders defined as ≥1 grade improvement from baseline, for month 1 (primary measurement time) Subject's FACE-Q Satisfaction with Cheeks, at the subject level rather than by treatment (because the questions are asked regarding the face rather than the treatment sides), for the 	

FACE-Q Rasch transformed score (0-100), which is converted from the sum score (range 5-20) across 5 items (symmetric, smooth, attractive, contour, and fullness), with each item scored on an ordinal scale from 1 to 4 (very dissatisfied, dissatisfied, satisfied, very satisfied); the FACE-Q Rasch score will be summarized for baseline and change from baseline to month 1 (primary measurement time)

[figure not shown]
Safety Assessments

- AEs, separately for AEs at cheeks, not at cheeks and combined
- Procedural Pain, based on subject assessment on an 11-point scale,
 response distribution by treatment, and paired treatment comparison

of each subject's difference score (-10 to +10)

• Injection Site Responses (ISR), based on subject's 30-day diary, overall and for each of 10 categories (redness, pain after injection, tenderness to touch, firmness, swelling, lumps/bumps, bruising, itching, discoloration and other), response distribution by treatment, separately for presence, severity (none, mild, moderate, severe), number of ISR days (none, 1-3, 4-7, 8-14 and 15 or more), and total duration (none, 1-3, 4-7, 8-14 and 15 or more days)

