5.1.1.2 Study Treatments

The following paired-comparison treatments are defined for this study:

- Study Treatment: JUVÉDERM VOLUMA® XC injectable gel using cannula
- Control Treatment: JUVÉDERM VOLUMA® XC injectable gel using needle

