5.1.2.9 Administration of Study Treatment

Variables related to administration of treatment will be summarized for safety population by treatment group as follows.

Table 5-12 Exposure to Study Treatment

Endpoint	Description	Timing	Methodology
Pretreatment	Separately for each of cannula	Treatment	Categorical
anesthesia type	and needle cheeks. Also,		Counts.
and duration	combined across cannula and		For injection
 Planes of 	needle for anesthesia type and		ease: responder
injection	number of injections.		descriptives with
• Injection			paired-
technique			comparison
Needle/cannula			difference and CI
used			
 Number of 			
injections			
Injection ease			

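### Does requiring anesthetic only on the cannula cheek mean the paired pain comparison must be relabelled and split by anesthetic match?

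*Protocol*

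**What the plan says.** Protocol 4.4.1 sets different rules for a subject's two cheeks. On the study side: "For the cheek treated with cannula, an anesthetic agent must be used on the treatment area prior to making the entry point". On the control side: "For the cheek treated with needle, use of anesthesia is optional, according to routine practice". The Synopsis repeats both rules. Topical and injectable agents are both acceptable, so the type of anesthetic, as well as its presence, can differ between cheeks.

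Pain during treatment is rated by the subject on an 11-point scale (Protocol 7.2), and SAP 4.1.1 acknowledges that this rating is unblinded. For pain, SAP Table 4-1 lists "response distribution by treatment, and paired treatment comparison" of the subject's difference score, which runs from -10 to +10. Protocol 8.3.4 treats pain descriptively. SAP 5.1.1.2 names the study side as "Study Treatment: JUVÉDERM VOLUMA® XC injectable gel using cannula" and the control side in the same form with the needle; neither name mentions anesthetic.

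Anesthesia is recorded. Protocol 7.4: "Treatment characteristics will be evaluated by collecting information on anesthesia usage injection volume, and injection ease". Protocol 12.4.1 puts the following in the subject's record, together with the pain rating: "Details of the injection procedure including anesthetic used, volume injected, ease of injection". SAP 5.1.2.9: "Variables related to administration of treatment will be summarized for safety population by treatment group as follows". The table below that sentence includes pretreatment anesthesia type and duration for each cheek.

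**The concern.** A measure meant to reduce pain is tied by rule to one of the two treatments being compared on pain. Randomizing which cheek gets the cannula balances side and order of treatment, but the anesthesia rule follows the device, so randomization cannot balance it. Pairing within the subject does not help either, because the imbalance is itself within the subject.

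A table headed cannula versus needle could then be read as showing that the cannula hurts less (or more), when part of the difference may come from the anesthetic. The per-cheek anesthesia counts do not show which subjects had the same anesthetic on both sides, and no readable section links anesthesia to the same subject's pain score. The apparent remedy is to relabel the contrast and add a pain table by anesthetic match.

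**Working it through.** The plan gives no figure to reproduce: no standard deviation, effect size or margin for pain, and no rate of anesthetic use on the needle cheek. The checks below use the 60 subjects planned for treatment (Protocol 5.1, SAP 4.1.2). All other inputs are assumptions.

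**1. Possible size of the anesthetic component.** Let q be the share of needle cheeks given no pretreatment anesthetic, and d the mean pain reduction it would have given there. If anesthetic only lowers the rating, the cannula-minus-needle mean moves by q × d in favor of the cannula.

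| q | d = 1 | d = 2 | d = 3 |
|---|---|---|---|
| 0 | 0 | 0 | 0 |
| 0.25 | 0.25 | 0.50 | 0.75 |
| 0.5 | 0.5 | 1.0 | 1.5 |
| 1 | 1 | 2 | 3 |

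The range is 0 to 3 points. It is zero if every needle cheek gets an equivalent anesthetic, which the protocol permits. Even the direction is an assumption, since part of the text describing the pain rating is redacted and what the rating covers is not fully known.

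**2. What depends on it.** The primary test concerns the blinded evaluator's volume-deficit score. The error control in SAP 5.1.3.2 covers the primary comparison and the responder comparison on that scale. Pain enters neither, so a shift of any size in the table above changes no study conclusion that the plan defines.

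**3. Do the per-cheek counts show matching?** Not always. Suppose cannula cheeks are 30 topical and 30 injectable, and needle cheeks are 20 topical, 20 injectable and 20 none. The largest number of same-type pairs is min(30, 20) + min(30, 20) = 40. The smallest is 0: the 30 topical cannula cheeks pair with 20 injectable and 10 none, and the 30 injectable with 20 topical and 10 none. If instead all 60 cannula cheeks are topical and needle cheeks are 40 topical and 20 none, there are exactly 40 matches. In both cases the number of needle cheeks with no pretreatment anesthetic can be read directly from the planned table.

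**4. What a table by match could show.** The 95% half-width for a mean paired difference is t(0.975, n-1) × SD / √n.

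| n | SD 1.5 | SD 2 | SD 3 |
|---|---|---|---|
| 60 (all) | 0.39 | 0.52 | 0.77 |
| 20 (60 / 3 strata) | 0.70 | 0.94 | 1.40 |
| 10 | 1.07 | 1.43 | 2.15 |

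For n = 20 and SD 2: 2.093 × 2 / 4.472 = 0.94. A stratum of 20 is thus resolved to about one point, the same order as much of the shift in step 1.

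**5. Whether matching isolates the device.** It does not, for three reasons.
- Needle-cheek anesthesia follows routine practice and is not randomized. As the left cheek is always treated first (Synopsis), it may also depend on pain felt on the first side.
- Matched pairs still differ in procedure. The cannula cheek has an entry point made with an introductory needle; Protocol 4.3.1 adds an optional, redacted item; and SAP Table 5-11 allows for volume given by both cannula and needle.
- The strata are hard to define. The gel contains lidocaine on both sides (Synopsis, test product), so a stratum labelled none would mean no pretreatment anesthetic only. A cheek given both topical and injectable agents fits no single type, and duration, which the SAP records, would be ignored.

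**The case for a change.** The best case for a change is that it costs almost nothing. The data are already collected, the anesthesia rule stays as it is, and the addition is a label, a three-row table of n, mean and SD without a test, and a footnote. Fixing the grouping before database lock would avoid choosing it after seeing the data. The SAP also goes beyond separate summaries for each side: it plans a paired difference under device-only names, which invites a device reading.

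The caution about interpretation stands. The contrast is between procedures, and step 3 shows that the per-cheek counts need not reveal matching. The case for the table does not stand: readers would be drawn to its matched row as the device effect, which is the misreading it is meant to prevent.

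Nor can silence in the SAP be counted against it. The methodology definitions under SAP 5.1.1.3 are not readable, and sections 5.1.5 and 5.2 and Tables 5-2 and 5-17 do not appear in the public text. Further detail on the pain analysis may sit there.

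**Conclusion.** No change to the plan is needed. The paired pain difference is a valid description of two procedures, each used under its own anesthesia rule, and nothing readable claims more. The anesthetic belongs to the cannula procedure as the protocol defines it, since it is required "prior to making the entry point with the introductory needle". Describing the procedures as they will be performed is a fair trade-off for a study whose objective is the safety and effectiveness of the gel given by cannula.

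The anesthetic component of the pain difference is unknown. It would be 0 to 3 points if q lies between 0 and 1, d between 1 and 3, and anesthetic only lowers the rating; none of these values comes from the documents. Whatever its size, it leaves the non-inferiority test untouched. When the pain table is reported, a sensible analyst would note that pretreatment anesthetic was required on one side and optional on the other, that the gel contains lidocaine on both, and that the difference is not attributable to the device alone, with a pointer to the per-cheek anesthesia summary. That is ordinary reporting practice and corrects no wrong result in the plan.

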4.4.2 Prohibited Medications/Treatments

Subjects must not initiate or be on an existing regimen of anti-coagulant medications (eg, warfarin, clopidogrel) [REDACTED]

[REDACTED]

During the course of the study, subjects must not:

- [REDACTED]
- [REDACTED]
- [REDACTED]
- [REDACTED]

Approval Date: 19-Oct-2017

[REDACTED]

[REDACTED]

[REDACTED]

[REDACTED]

[REDACTED]

The decision to administer a prohibited medication/treatment is done with the safety of the study participant as the primary consideration. When possible, Allergan is to be notified before the prohibited medication/treatment is administered.

4.4.3 Special Diet or Activities

Within the first 24 hours after treatment, it is recommended that subjects avoid strenuous exercise, extensive sun or heat exposure, and alcoholic beverages. Exposure to any of the above may cause temporary redness, swelling, and/or itching at the injection sites.

For 2 days after treatment, it is recommended that subjects avoid unnecessary external compression of the treatment site that could cause displacement or indentation where the product has been placed.

For 1 week after treatment, subjects will be advised not to have a massage, enter a hot spring or sauna, or go swimming.

4.5 Treatment Allocation Ratio and Stratification

Subjects will be randomized in a 1:1 ratio to receive treatment on the first side with the cannula or needle.

5. Study Population

5.1 Number of Subjects

Up to 75 subjects will be enrolled at up to 7 sites in order to have 60 subjects treated.

5.2 Study Population Characteristics

Adult subjects who are seeking correction of age-related volume deficit in the mid-face will be recruited.

[REDACTED]

[REDACTED]
[REDACTED]
[REDACTED]
[REDACTED]
[REDACTED]
[REDACTED]

- 8. Has experienced trauma to the mid-face area within 6 months before enrollment or has residual deficiencies, deformities, or scarring

[REDACTED]

- 10. Has a history of anaphylaxis or allergy to lidocaine (or any amide-based anesthetics), HA products, or *Streptococcal* protein, or is planning to undergo allergen desensitization therapy during the term of the study

- 11. Has active autoimmune disease

- 12. Has current cutaneous or mucosal inflammatory or infectious processes (eg, acne, herpes, gum disease), abscess, an unhealed wound, or a cancerous or precancerous lesion, above the subnasale

[REDACTED]
[REDACTED]

[REDACTED]
[REDACTED]
[REDACTED]
[REDACTED]
[REDACTED]

[REDACTED]

[REDACTED]
[REDACTED]
[REDACTED]
[REDACTED]

[REDACTED]

Approval Date: 19-Oct-2017

[Redacted]

[Redacted]

[Redacted]

[Redacted]

[Redacted]

[Redacted]	[Redacted]

[Redacted]

[Redacted]	[Redacted]
[Redacted]	[Redacted]

[Redacted]

[figure not shown]
[Redacted]

[Redacted]

Approval Date: 19-Oct-2017

[Redacted text block]

Approval Date: 19-Oct-2017

Approval Date: 19-Oct-2017

[Redacted text block]

6.3 Instructions for the Subjects

During each study visit, subjects will be required to remove all makeup to avoid interference with the assessments.

[Redacted text block]

Approval Date: 19-Oct-2017

[REDACTED]

For at least 24 hours after treatment, it is recommended that subjects avoid strenuous exercise, extensive sun or heat exposure, and alcoholic beverages to reduce the risk of posttreatment redness, swelling, and/or itching.

Subjects will also be instructed to contact the TI or his/her research staff to report any unexpected symptoms or to ask questions about the study.

6.4 Unscheduled Visits

An unscheduled visit may occur for safety purposes (eg, evaluation of AEs or injection site responses [ISRs] as requested by the subject and/or TI). Applicable procedures will be performed and recorded on the eCRF.

6.5 Early Discontinuation of Subjects

Each subject reserves the right to withdraw from the study at any time without jeopardy to his/her future medical care. It is recommended that all follow-up procedures scheduled to be performed at the final site visit be performed at the subject's last site visit. Subjects may also be administratively withdrawn if they do not return for follow-up visits. For any subject who withdraws from the study, the date and reason for withdrawal will be recorded on the eCRF. If a treatment-related AE is ongoing at the time of withdrawal, the TI will attempt to follow the subject until the AE has been resolved or follow-up is no longer possible. The TI shall ask for the subject's permission to follow his/her status/condition outside the study.

Randomized subjects who withdraw before treatment will not be replaced by another subject. The subject number and associated randomization number of the withdrawn subject must not be reassigned to a different subject.

If a subject fails to return for 1 or more scheduled study visits, the TI (or designee) will attempt to contact the subject to determine and document the reason the subject has failed to return and to encourage compliance with the study visit schedule.

At regular intervals, the TI (or designee) will record on the eCRF the reasons for which any subjects are discontinued from the study, including subjects who signed the ICF but do not proceed to randomization.

6.6 Withdrawal Criteria

The subject may withdraw at will at any time for any reason.

If a subject has a positive urine pregnancy test prior to treatment, the subject will not be eligible for treatment and will be withdrawn from the study. If a subject has a positive urine pregnancy test after treatment, she will continue all scheduled visit procedures. The pregnancy will be followed as described in Section 10.3.

7. Response Measures and Summary of Data Collection Methods

7.1 Effectiveness Measures

7.1.1 Primary Effectiveness Measure

The primary effectiveness measure is the blinded EI's assessment at Month 1 of the subject's overall mid-face volume deficit for each cheek on the validated 6-point photonumeric MFVDS described in Table 2.

Table 2 Midface Volume Deficit Scale

Score	Grade	Description
5	Severe	
 • Wasting • Severe concavity in the zygomaticomalar region, anteromedial region, and/or submalar region • Severe tear troughs and/or nasolabial folds • Significant nasojugal folds and/or prejowl sulcus • Significant prominence of bony landmarks • Significant visibility of underlying musculature
4	Significant	
 • Significant concavity in the zygomaticomalar region, anteromedial region, and/or submalar region • Significant tear troughs and/or nasolabial folds • Moderate nasojugal folds and/or prejowl sulcus • Moderate prominence of bony landmarks • Moderate visibility of musculature
3	Moderate	
 • Moderate concavity in the zygomaticomalar region, anteromedial region, and/or submalar region • Moderate tear troughs and/or nasolabial folds • Mild nasojugal folds and/or prejowl sulcus • Mild prominence of bony landmarks • Mild visibility of musculature
2	Mild	
 • Mild concavity in the zygomaticomalar region, anteromedial region, and/or submalar region • Mild tear troughs and/or nasolabial folds

Score	Grade	Description
1	Minimal	
 • Flattening in the zygomaticomalar region, anteromedial region, and/or submalar region
0	None	
 • Moon face • Fullness (convexity) in the zygomaticomalar region, anteromedial region, and/or submalar region

7.1.2 Secondary Effectiveness Measure

The secondary effectiveness measure is the validated 5-item Satisfaction with Cheeks module of the FACE-Q questionnaire evaluated by the subject (very dissatisfied, somewhat dissatisfied, somewhat satisfied, very satisfied).

7.2 Safety Measures

Safety measures will include:

- subject assessment of procedural pain during treatment on an 11-point scale [REDACTED]
- presence and severity (mild, moderate, or severe) of ISRs recorded by subjects in daily safety diaries for 30 days after treatment
- AEs observed by the TI or reported to the TI by the subject

The subject's daily safety diary will list the following ISRs that have been reported previously with HA dermal filler injections:

- redness
- pain after injection
- tenderness to touch
- firmness
- swelling
- lumps/bumps
- bruising
- itching
- discoloration

AEs will be monitored continuously throughout the study and documented on an AE eCRF.

